7.2.2 Down-Titration Period

All subjects who have received ≥ 4 doses of BRV during either the IOB Treatment Period or the iv PK Period and who will not continue BRV will have their BRV dose reduced by a maximum of half the dose every week for a maximum of 4 weeks until a dose of 1mg/kg/day (50mg for subjects with body weights ≥ 50 kg) is reached. Subjects who have received < 4 doses of BRV may have BRV down titrated at the discretion of the Investigator. Subjects not able to receive oral BRV for down titration, may receive iv BRV for down titration. In the later circumstance, the subjects may receive more than 10 consecutive doses of iv BRV in accordance with the Investigator's discretion.

The OLB subjects who discontinue BRV during the Screening Period will return to the long-term, open-label study for down titration of BRV.

7.3 Packaging

Primary packaging:

- Tablets for oral administration: high-density polyethylene bottles with child-resistant closure containing tablets of BRV 10mg, 25mg, 50mg, 75mg, and 100mg
- Oral solution: 300mL amber glass bottles with child-resistant closure
- Solution for iv injection: 6mL clear Type I glass vials with bromobutyl rubber stopper containing 5mL (50mg) of BRV

7.4 Labeling

Clinical drug supplies will be labeled in accordance with the current International Council for Harmonisation (ICH) guidelines on Good Clinical Practice (GCP) and Good Manufacturing Practice and will include any locally required statements. If necessary, labels will be translated into the local language.

7.5 Handling and storage requirements

The Investigator (or designee) is responsible for the safe and proper storage of IMP at the site. Investigational medicinal product stored by the Investigator is to be kept in a secured area with limited access according to the storage conditions mentioned on the label. Additional information pertaining to the handling of BRV, a Schedule V drug, is provided in the IMP Handling Manual.

Appropriate storage conditions must be ensured either by controlling the temperature (eg, room, refrigeration unit) or by completion of a temperature log in accordance with local requirements on a regular basis (eg, once a week), showing actual and minimum/maximum temperatures reached over the time interval.

In case an out-of-range temperature is noted, it must be immediately reported as per instructions contained in the IMP Handling Manual.

7.6 Drug accountability

A Drug Accountability form will be used to record IMP dispensing and return information on a by-subject basis and will serve as source documentation during the course of the study. Details of any IMP lost, damaged (due to breakage or wastage), not used, partially used, disposed of at the study site, or returned to the Sponsor or designee must also be recorded on the appropriate forms. All supplies and pharmacy documentation must be made available throughout the study for UCB (or designee) to review.

The Investigator (or designee) is responsible for retaining all used, unused, and partially used containers of IMP until returned or destroyed, taking into account local laws and regulations.

The Investigator may assign some of the Investigator's duties for drug accountability at the study site to an appropriate pharmacist/designee.

The Investigator must ensure that the IMP is used only in accordance with the protocol.

Periodically, and/or after completion of the clinical phase of the study, all used (including empty containers)/partially used, unused, damaged and/or expired IMP containers must be reconciled and either destroyed at the site according to local laws, regulations, and UCB standard operating procedures (SOPs), or returned to UCB (or designee). Investigational medicinal product intended for the study cannot be used for any other purpose than that described in this protocol.

7.7 Procedures for monitoring subject compliance

At each visit after IMP is dispensed, subjects/guardians must return all unused IMP and empty IMP containers. Drug accountability must be done in the subject's presence in order to obtain explanations regarding discrepancies in compliance with the dosing regimen. Drug accountability must be recorded on the Drug Accountability form.

Site personnel who are administering iv BRV will record information about all doses administered, including the target dose, actual dose administered, and the dates and times of initiation and completion of each iv administration. If the actual dose is less or more than the target dose, the reason a partial or excessive dose was administered will be recorded.

Intravenous solution will be administered under supervision of the Investigator or his/her designee. The noninjected volume will be recorded in the CRF. Compliance with the

recommended duration of the iv administration will also be assessed by recording the start time and the stop time in the CRF.

Subjects who receive <75% or >125% of the planned BRV dose will be considered noncompliant. If a subject is found to be persistently noncompliant in the Investigator's opinion, the Sponsor, in conjunction with the Investigator, will make a decision as to whether the subject should be withdrawn from the study.

7.8 Concomitant medication(s)/treatment(s)

For any treatment other than the IMP, including over-the-counter products, an accurate record must be kept in the clinic chart (source documentation) and in the CRF. Concomitant medications should be recorded on the concomitant AED page or the concomitant non AED medication page of the CRF, according to the indication. New medications should be recorded in the CRF at only the first visit at which they are reported and subsequently only if there is a change. For any change, the start date corresponding to the date of change in administration should be recorded in the CRF.

7.8.1 Permitted concomitant treatments (medications and therapies)

All treatments are permitted with the exception of those listed in Section 7.8.2.

Vagus nerve stimulation is allowed and will be counted as a concomitant AED. A stable ketogenic diet is allowed.

7.8.2 Prohibited concomitant treatments (medications and therapies)

The following concomitant medication is prohibited during the study:

- Levetiracetam

7.8.3 Rescue medication

Investigators may administer rescue medication in accordance with medical judgment at any time during the study. No rescue medication will be supplied by UCB.

7.9 Blinding

This is an open-label study; no blinding is required.

7.10 Randomization and numbering of subjects

Subjects will not be randomized in EP0065.

For OLB subjects, the unique identification number assigned to them in the open-label study will be used to identify them and maintain subject confidentiality throughout EP0065.

The RxB, IOB, and IIB subjects will be assigned a unique identification number for identification and to maintain subject confidentiality. To enroll these subjects, the Investigator or designee will contact the IRT and provide brief details about the subject to be enrolled. Each subject will receive a 5-digit number assigned at screening that serves as the subject identifier throughout the study. The subject number will be required in all communication between the Investigator or designee and the IRT regarding a particular subject. Subject numbers and kit numbers will be tracked via the IRT.

8 STUDY PROCEDURES BY VISIT

Days are provided relative to Day 1, the first day of the iv PK Period.

8.1 Visit 1 (Day -10 to Day-1 for OLB, RxB, and IIB subjects; Day -20 to Day -11 for IOB subjects)

- Signing and dating of written ICF by parent(s)/legal representative(s)
- Signing and dating of Assent form by the subject (if applicable, according to age and local requirements)

The following assessments should be performed only after the ICF and Assent form (if applicable) procedures described immediately above are completed:

- Subject identification card dispensing
- Inclusion/exclusion criteria
- Demographic data
- General medical/procedure history
- Historical seizure count
- Prior and concomitant medications including AEDs
- Physical examination (complete)
- Neurological examination (complete)
- Body weight (before BRV dispensed)
- Body height
- Vital signs (BP, pulse rate, RR, and temperature)
- 12-lead ECG
- Clinical chemistry, hematology, and endocrinology
- Urinalysis for subjects for whom urine sample collection is feasible
- Pregnancy testing for females of childbearing potential (urine test)
- AEs
- C-SSRS (for subjects ≥ 6 years of age); version per [Section 10.3.3](#)

8.2 Visit 2 (Day -10 to Day -1; IOB subjects only)

- Inclusion/exclusion criteria (before BRV dispensed)
- Concomitant medications including AEDs
- Body weight (before BRV dispensed)
- Vital signs BP, pulse rate, RR, and temperature
- Pregnancy testing for females of childbearing potential (urine)

- AEs
- C-SSRS (for subjects ≥ 6 years of age); version per [Section 10.3.3](#)
- Withdrawal criteria
- Dispense oral BRV

8.3 Visit 3 (Day 1) through Visit 12 (Day 6)

- Inclusion/exclusion criteria (Visit 3 only; prior to iv BRV administration)
- Concomitant medications including AEDs
- Physical examination (brief) (at Visit 3 prior to the initial dose of BRV and daily thereafter, ideally after the morning dose of BRV each day)
- Tanner staging at Visit 3 prior to iv BRV administration only. The Investigator should use clinical judgment in deciding which subjects are selected for evaluation of Tanner Stage (ie, those subjects who are pubescent).
- Neurological examination (brief) (at Visit 3 prior to iv BRV administration and daily thereafter, ideally after the morning dose of BRV each day)
- Body weight (Visit 3 only, prior to iv BRV administration)
- Body height
- Vital signs (BP, pulse rate, RR, and temperature) (see [Table 5-2](#) and [Table 5-3](#) for timing relative to initiation of iv BRV administration). The criteria for BP values to be low or high PCS values are described in [Table 10-6](#).
- 12-lead ECG (see [Table 5-2](#) and [Table 5-3](#) for timing relative to initiation of iv BRV administration)
- Pregnancy testing for females of childbearing potential (urine test) (Visit 3 only, prior to iv BRV administration)
- AEs
- Withdrawal criteria
- C-SSRS (for subjects ≥ 6 years of age); version per [Section 10.3.3](#) (Visit 3 prior to iv BRV administration and, for subjects who receive ≥ 2 doses of iv BRV and who will enter the Down-Titration Period, at their final visit of the iv PK Period [Visit 4 to 12, as applicable])
- PK sampling (see [Table 5-2](#) and [Table 5-3](#) for timing relative to initiation of iv BRV administration)
- Collect oral BRV (as needed for IOB subjects who will enter the long-term, open-label study)
- Dispense oral BRV (at final visit of this period and only for subjects who will enter the Down-Titration Period)
- iv BRV administration

Subjects who are continuing into the long-term, open-label study after their final dose of iv BRV, will re-enter (OLB subjects)/enter (RxB, IOB, and IIB subjects) that study at the completion of assessments associated with the final iv dose of iv BRV.

8.4 TC-1 (Day 2 to Day 9) (all subjects who received iv BRV)

Telephone Contact-1 (TC-1) should occur 1 to 3 days after the final dose of iv BRV. The primary purpose of this contact is to collect information pertaining to possible infusion-related AEs. Subjects who report new or worsened infusion-site related AEs should return for an Unscheduled Visit as soon as possible.

- Concomitant medications including AEDs
- AEs
- Withdrawal criteria

8.5 TC-2

Telephone Contact-2 is only applicable to subjects who participate in the Down-Titration Period for more than 2 weeks; TC-2 should be conducted approximately half way through the Down-Titration Period.

- Concomitant medications including AEDs
- AEs
- Withdrawal criteria

8.6 Visit 13

This visit is applicable only to subjects who have participated in the Down-Titration Period or to subjects who need to withdraw from the study and do not need to have BRV down titrated.

- Concomitant medications including AEDs
- Physical examination (brief)
- Neurological examination (brief)
- Body height
- Vital signs (BP, pulse rate, RR, and temperature)
- 12-lead ECG
- Clinical chemistry, hematology, and endocrinology
- Urinalysis for subjects for whom urine sample collection is feasible
- Pregnancy testing for females of childbearing potential (urine test)
- AEs
- C-SSRS (for subjects ≥ 6 years of age); version per [Section 10.3.3](#)
- Collect oral BRV

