4.2.2 Other safety variables

- 12-lead ECG values before, during, and after each iv BRV administration
- BP, pulse rate, RR, and temperature values before, during, and after each iv BRV administration
- Clinical laboratory parameters (hematology, chemistry, and endocrinology) pre and posttreatment
- Urinalysis parameters pre and posttreatment

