5 STUDY DESIGN

5.1 Study description

EP0065 is a Phase 2 multicenter, open-label study to evaluate the PK, safety, and tolerability of iv BRV administered as a 15-minute iv infusion and an iv bolus (up to 2-minute infusion) in subjects ≥ 1 month to < 16 years of age with epilepsy.

It is planned for approximately 50 enrolled subjects to receive iv BRV in the following age-based cohorts (approximately 12 subjects/cohort):

- Cohort 1: ≥ 12 to < 16 years
- Cohort 2: ≥ 6 years to < 12 years
- Cohort 3: ≥ 2 to < 6 years
- Cohort 4: 1 month to < 2 years

The following subjects will be eligible for enrollment in EP0065:

- QLB subjects: currently receiving oral BRV as participants in a long-term, open-label study
- RxB subjects: currently receiving prescribed oral BRV from commercial supply
- IOB subjects: not currently receiving BRV; first dose of BRV in EP0065 will be oral tablet or solution
- IIB subjects: not currently receiving BRV; first dose of BRV in EP0065 will be by iv infusion

For OLB and RxB subjects, the maximum BRV dose is 5mg/kg/day (rounded). For IOB and IIB subjects, the maximum BRV dose is 4mg/kg/day. **Throughout the study, no subject may receive a dose greater than BRV 200mg/day.** Subjects will receive oral BRV (tablets or oral solution) in equally divided doses; BRV oral solution may be given by enteric administration (eg, by feeding tube) based on subject need.

The EP0065 study periods and visits are described below. The PK assessments will be made during the iv PK Period only and safety data will be collected throughout the study, with intensive collection of safety data with each iv BRV dose administered. A Schedule of Study Assessments is provided for the Screening through iv PK Periods in [Table 5-1](#) and for the Down-Titration Period and Safety (BRV-free) Periods (for subjects not continuing BRV) in [Table 5-4](#).

Screening Period (1 to 10 days)

During the Screening Period, the OLB and RxB subjects will continue treatment with oral BRV using their assigned open-label study supply or prescribed commercial supply, respectively. The IOB and IIB subjects will not receive BRV during this period.

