12.8 Determination of sample size

The primary objective of the study is to evaluate the PK, safety, and tolerability of BRV given intravenously. The plan for approximately 50 enrolled subjects (4 cohorts of approximately 12 subjects each) to receive iv BRV was deemed clinically appropriate for the evaluation of the PK, safety, and tolerability of iv BRV administration in subjects ≥ 1 month to < 16 years of age with epilepsy. No formal sample size calculation has been performed.

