## 10 SAFETY ANALYSIS

All analyses for extent of exposure and safety are performed for the SS-iv. Selected tables will be performed on the SS.

Inferential statistical tests are not planned for the safety variables.

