### 10.4 Clinical laboratory evaluations

#### 10.4.1 Hematology, Chemistry and Urinalysis Parameters

Laboratory values will be collected according to the protocol schedule of study assessments. In case a laboratory test is repeated at one visit, the latest measurement will be used for summary

tables. For continuous laboratory variables (including hematology and chemistry) summary statistics of Baseline values, Visit 13 values, and change from Baseline will be presented overall and by age cohort, for all subjects, and by infusion duration at each study visit for the SS-iv. For categorical urinalysis laboratory variables summary statistics of Visit 1 and Visit 13 values will be presented overall and by age cohort, for all subjects, and by infusion duration for the SS-iv.

Shifts from Baseline to Visit 13 based on the normal range (ie, low, normal, high, and missing) for each hematology, and chemistry lab parameter will be presented for subjects who have a Baseline and Visit 13 measurement overall and by age cohort, for all subjects and by infusion duration for the SS-iv. Shifts from Baseline to Visit 13 based on the categorization of each urinalysis lab parameter will be presented for subjects who had done a Baseline and Visit 13 measurement, overall and by age cohort, for all subjects and by infusion duration for the SS-iv.

The number and percentage of subjects with possibly clinically significant treatment-emergent (PCST) for each laboratory variable (i.e. PCST low value, PCST high value) for hematology, biochemistry (including Thyroxine (T4)) and urinalysis will be summarized overall and by age cohort, for all subjects, and by infusion duration. The criteria for a laboratory value to be PCST is defined in [Appendix 12.2](#), but note, only laboratory variables that meet PCST criteria at Visit 13, but not Baseline will be considered as PCST.

The number of occurrences of each unique PCST type will be tabulated by timepoint within each visit within each subject, and include relevant criterion: gender, age, race, timepoint, visit, subject group and infusion duration. In addition, the number of subjects with at least one PCST will be displayed for each age cohort.

The following listings will be provided: all laboratory results of clinical chemistry, hematology, urinalysis including an indicator as to which met the criteria for PCST. A separate listing will contain all additional laboratory tests performed and sample takes.

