## **10.5 Vital signs, physical findings, and other observations related to safety**

### **10.5.1 Vital signs and body weight**

Vital signs (systolic blood pressure [SBP], diastolic blood pressure [DBP], respiratory rate [RR], temperature, pulse rate) and body weight will be collected according to the protocol schedule of study assessments.

Observed values of body weight will be summarized for each visit by infusion duration, and by subject group for the SS-iv.

Observed values of SBP, DBP, RR, temperature and pulse rate will be summarized for each time point (as defined in [Section 4.8](#)) within each visit. Change from Baseline for SBP, DBP, RR, temperature, and pulse rate will be summarized for all post-Baseline time points within each visit. Tables will be provided overall and by age cohort, for all subjects and by infusion duration, and by subject group for the SS-iv. Observed values for SBP, DBP, RR, temperature, and pulse rate at each timepoint will be plotted as a line for each subject in line graphs by visit (Visit 1 to 3, then for each visit individually i.e. Visit 4, 5, etc), age cohort and infusion duration. Abnormal values defined by the PCST criteria will be marked using symbols.

Vital signs PCS/PCST definitions are located in [Appendix 12.2.4](#). Vital signs PCST events (i.e. Treatment-emergent vital signs PCS) are defined as events which started on or after the first BRV medication taken during the EP0065 study that meet PCS criteria. Subjects who began the study on BRV treatment (OLB and RxB subjects) will be assumed to have taken BRV treatment on the first day of screening. Therefore, timing of a PCS being treatment emergent (i.e. a PCST) varies by subject group: all PCS are treatment emergent for RxB and OLB subjects; all PCS on or after the IOB Treatment Period are treatment emergent for IOB subjects; all PCS on or after the iv PK Period are treatment emergent for IIB subjects.

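### SAP 10.4.1 pools laboratory changes from children on BRV at Baseline with changes from children BRV-free at Baseline, so contrasts of opposite direction are averaged and the group summaries promised in Protocol 12.4.1 are missing

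*Protocol*

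**What the plan says.** **Sampling.** Blood laboratory tests are scheduled at Visit 1 (Protocol Table 5-1, section 8.1) and Visit 13 (Table 5-4, section 8.6). None is scheduled in the iv PK Period (section 8.3). Of Visit 13, Protocol 8.6 says "This visit is applicable only to subjects who have participated in the Down-Titration Period or to subjects who need to withdraw from the study", the latter where no down-titration is needed. SAP 2.2.2.2 accepts that post-treatment values will exist only for Visit 13 attendees. Protocol 4.2.2 names the variable as "Clinical laboratory parameters (hematology, chemistry, and endocrinology) pre and posttreatment".

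**BRV state at Visit 1.** During Screening, "the OLB and RxB subjects will continue treatment with oral BRV using their assigned open-label study supply or prescribed commercial supply" (Protocol 5.1). IOB and IIB children take no BRV in that period.

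**Analysis.** SAP 3.4 sets Baseline as the latest value before the first iv infusion and allows unscheduled central-laboratory values. For continuous laboratory variables, SAP 10.4.1 says that "Visit 13 values, and change from Baseline will be presented overall and by age cohort, for all subjects, and by infusion duration". The shift and PCST-percentage tables have the same layout. The PCST rule is that "only laboratory variables that meet PCST criteria at Visit 13, but not Baseline will be considered as PCST". A separate per-subject tabulation of laboratory PCST occurrences does show subject group.

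**Elsewhere.** For observed vital signs and their change, SAP 10.5.1 says "Tables will be provided overall and by age cohort, for all subjects and by infusion duration, and by subject group for the SS-iv"; SAP 10.5.2 does the same for ECG. Protocol 12.4.1 promises additional safety summaries of OLB, RxB, IOB and IIB by cohort and infusion duration, and SAP 4.7 says most summaries will be given by subject group. SAP 3.10, which lists changes from the protocol analysis, is silent on dropping this for laboratory data.

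**The concern.** Change from Baseline means different things in the two halves of the table. For OLB and RxB children it compares a value on oral BRV with one after tapering or stopping. For IOB and IIB children it normally compares a BRV-free value with one taken under residual or past exposure. If BRV moves a marker up, the first change tends to be negative and the second positive. Averaging them can shrink, cancel or reverse a real effect, and the shift tables mix the same two directions.

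The PCST rule adds an asymmetry. In an OLB or RxB child, an abnormality already present on BRV at Baseline can never count as a laboratory PCST. For vital signs and ECG, SAP 10.5.1 and 10.5.2 assume that the same children are on BRV from the first Screening day and count all their PCS values as treatment-emergent.

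**Working it through.** **Stated figures.** There is no power calculation to reproduce: "No formal sample size calculation has been performed" (Protocol 12.8). The figures that bear on the timing of Visit 13 are the maximum durations in Protocol 5.1.1, and both reproduce:

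- Study: 10 Screening + 10 IOB Treatment + 6 iv PK + 28 down-titration + 14 BRV-free = 68 days.
- BRV, IOB: 10 + 6 + 28 = 44 days. For OLB/RxB, counting Screening oral BRV: 10 + 6 + 28 = 44 days.

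The 14 BRV-free days follow the last dose. Table 5-4 puts Visit 13 in the Down-Titration column and only TC-3 in the BRV-free column.

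**Inputs for the pooling check.** None of these is in the documents:

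- d: shift in a marker while on BRV, the same in all groups.
- f: fraction of d still present at Visit 13 (0 to 1), the same in all groups.
- p: share of OLB/RxB among children with both Baseline and Visit 13 values (0 to 1).

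**Formula.** With BRV-free level b:

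- OLB/RxB: (b + fd) − (b + d) = (f − 1)d
- IOB/IIB: (b + fd) − b = fd
- Pooled: p(f − 1)d + (1 − p)fd = (f − p)d

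**Pooled mean change, in units of d**

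| p | f = 0 | f = 0.25 | f = 0.50 | f = 1 |
|---|---|---|---|---|
| 0 | 0 | 0.25 | 0.50 | 1.00 |
| 0.10 | −0.10 | 0.15 | 0.40 | 0.90 |
| 0.25 | −0.25 | 0 | 0.25 | 0.75 |
| 0.50 | −0.50 | −0.25 | 0 | 0.50 |

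The pooled figure differs from the IOB/IIB change by −pd. It is attenuated for 0 < p < f, zero at p = f, and of the wrong sign for p > f. With few attendees p moves easily: 2 OLB/RxB children among 8 would give p = 0.25.

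**Plausible f, as illustration only.** If an effect tracked dose and Visit 13 fell at the taper end point of 1 mg/kg/day (Protocol 7.2.2), starting from 2, 4 or 5 mg/kg/day gives f = 1/2 = 0.50, 1/4 = 0.25 or 1/5 = 0.20.

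**After separation by BRV state at Baseline**

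| f | OLB+RxB | IOB+IIB |
|---|---|---|
| 0 | −1.00d | 0 |
| 0.25 | −0.75d | +0.25d |
| 0.50 | −0.50d | +0.50d |

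**Would the SAP's own grouping do?** SAP 3.1 combines OLB, RxB and IOB against IIB. If IOB is a share q of the combined group, its mean change is (1 − q)(f − 1)d + qfd = (f − 1 + q)d. At f = 0.25 this gives −0.75d, −0.50d, −0.25d, 0 and +0.25d for q = 0, 0.25, 0.50, 0.75 and 1. The mixing remains, because IOB children are BRV-free at Visit 1.

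**The case against.** The strongest reply is that the SAP is coherent on its own terms. Study medication is iv BRV only (SAP 2.3, 3.2.6), so for a child switched mg-to-mg from oral BRV the on-oral value is a proper pre-iv reference. Laboratory values are secondary to AEs and AE withdrawals, and "Inferential statistical tests are not planned for the safety variables" (SAP 10). On-BRV abnormalities at Visit 1 still appear in the Baseline summaries, the Baseline categories of the shift tables and the listings; PDILI is summarised at any visit. Visit 13 attendees from about 50 children, spread over four cohorts and two infusion durations, will leave very small cells.

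Most of this stands and limits the importance of the point. It does not remove it: Visit 13 is not a value on iv BRV at the previous dose, so the change does not measure that pre-iv reference against iv exposure.

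A reader might infer more than the documents support:

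- *Laboratory output has no subject-group information.* Not so: the per-subject PCST tabulation carries it.
- *Visit 13 is BRV-free.* Not established. It sits in the Down-Titration column, and no time since last dose is set for children who withdraw without tapering.
- *Vital signs and ECG are fully split.* Their PCST-percentage tables have no subject-group split either.
- *OLB/RxB Visit 13 PCSTs should lose the treatment-emergent label.* That would conflict with the SAP's convention for these children and remove a flag from an abnormality first seen after iv BRV.
- *Visit 1 is always the Baseline.* An unscheduled central-laboratory value can replace it, and for an IOB child it could be taken on oral BRV.

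**Conclusion.** The point holds as a defect of table layout and labelling. Three parts need no numerical assumption: the only scheduled laboratory contrast runs in opposite directions by BRV state at Baseline; the change, shift and PCST-percentage tables pool the two; and this drops a four-group summary promised in Protocol 12.4.1 without an entry in SAP 3.10.

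The size, (f − p)d, is conditional. It assumes the same d and f in long-term users and in children who may have had only one or two iv doses. It would be tempting to conclude that the pooled tables will hide or reverse a BRV effect, but the documents give neither f nor p. The share p may be low, since OLB children who continue BRV re-enter the long-term study (Protocol 8.3) and those who discontinue during Screening taper there (Protocol 7.2.2). At p = 0.10 the shift is only 0.10d. OLB and RxB children who stop BRV later can still reach Visit 13, so p cannot be taken as zero. The primary safety variables are unaffected.

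**What to change.** In SAP 10.4.1, present the laboratory change-from-Baseline, shift and PCST-percentage tables additionally by actual BRV state at Baseline. This is normally OLB+RxB versus IOB+IIB; an IOB child whose Baseline value was drawn on oral BRV goes with the on-BRV group. Do not use the OLB+RxB+IOB versus IIB grouping here.

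- Show n and days since last BRV dose at Visit 13 in each column.
- Label the OLB/RxB contrast *on BRV at Baseline to tapered or stopped*.
- Keep the treatment-emergent label on their Visit 13 PCSTs and add the flag *on BRV at Baseline*.
- If the four-group summary of Protocol 12.4.1 is still not produced for laboratory data, list that in SAP 3.10.

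The cost is SAP wording and a few table columns on data already collected. The downside is small cells, some possibly empty; showing n makes that visible.
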